2.4 Recruitment Plan

Subjects will be recruited from the IBD Program at Children's National Medical Center, and from other sites via provider communication. The trial will be listed at clinicaltrials.gov.

2.5 Informed Consent

The informed consent process will be conducted in a private room to respect subject privacy. Following the briefing of the research study, the coordinator or designee will provide the subject with ample time to read the consent, and will answer any of their questions regarding the document. No study procedures will occur before the subject gives informed consent. To minimize any possible coercion, supervisors or anyone in a dominant position will not be permitted to consent the subject. The treating physician is responsible for ensuring that written informed consent, including written authorization for use and disclosure of PHI and appropriate signatures and dates, is obtained from each patient before any protocol-related procedures, including any pre-treatment procedures, are performed. All patients who are <18 years of age will require a parental or legal guardian signature of informed consent. In addition, all patients between the ages of 12 and 17 years will require a signature of assent.

Prior to the subject's participation in any trial procedures, the investigator or designee will ensure that the potential participant understands the research study and their role in the study. The written informed consent will be signed and dated by the subject and by the person who conducted the informed consent discussion. A signed copy of the consent form will be placed in the subject's trial chart and a photocopy will be given to the subject. Informed consent will be obtained in accordance with the Code of Federal Regulations (CFR) 21 CFR 50.25, 32 CFR 219, 45 CFR 46 and 15-2, ICH Harmonized Tripartite Guidance for Good Clinical Practice, and the Belmont Report. Also included in the consent process, Health Insurance Portability Accountability Act (HIPAA) authorization will be obtained before any study procedure is undertaken.

If subject decides to take part in the research study, their protected health information will not be given out except as allowed by law. Study personnel will work hard to keep this information private. The results of the data from the study may be published. However, subject will not be identified by name.

Subjects may change their mind and withdraw from the study any time they want.

If they decide to stop taking part in the study or if they are removed from the study, they may decide that they no longer allow protected health information that identifies them to be used in this research study. The study staff will respect the subject's decision to

decline access to their medical records and biological samples. Subject decision will be available in their records.

If subject agrees to participate in this research study, the research team (PI, co-investigators, Clinical Research Manager, statistician, Clinical Research Coordinator, Quality Assurance coordinator, and Research Nurse), the research sponsor (when applicable) and the sponsor's representatives, may use coded study data. The coded study data does not include subject name, address, telephone, or social security number. Instead, the researcher assigns a code to the data. The research team or the research sponsor may share the coded study data with others to perform additional research, place it into research databases, share it with researchers in the U.S. or other countries, or use it to improve the design of future studies. They may also publish it in scientific journals, or share it with business partners of the sponsor and to file applications with U.S. or foreign government agencies to get approval for new drugs or health care products.

The research team would store personal health information collected from the study in a database in a password protected computer for future research. The database is maintained by Children's National Medical Center in the division of Blood and Marrow Transplantation.

2.6 Eligibility criteria

2.6.1 Subject Inclusion Criteria

- For the young adult cohort, patients must be ages 17 ≤22 years
- For the pediatric cohort, patients must be ages 12 ≤16 years
- Patients must have moderate-severely active CD or UC (defined in section 2.3), and documented active disease on flexible sigmoidoscopy, colonoscopy or MR enterography within the preceding 2 months.
- Patients who have failed or are intolerant of biologic therapy. Specifically, the patient will have recurrence or persistence of active disease despite current or past treatment with a biologic. At the time of enrollment, study subjects may be currently receiving 5-aminosalicylates, corticosteroids (≤ 20 mg daily or up to 0.5 mg/kg/day if weight <40 kg), methotrexate, 6MP/azathioprine, or a biologic (either as monotherapy or in combination). During the treatment phase, if the treating physician thinks that a medication dose should be lowered to avoid side effects, this should be recorded.
 - Patient or parent/guardian capable of providing informed consent.
-

2.6.2 Subject Exclusion Criteria

- Patient <12 years of age or >22 years of age
- Pregnant or breastfeeding. Serum pregnancy test must be negative at screening for female subjects of childbearing potential. Urine pregnancy test must remain negative at each of 4 infusion visits.

- Patients with toxic mega-colon or intestinal perforation
- Evidence of autoimmune chronic active hepatitis or sclerosing cholangitis.
- Patients with fever > 39° C or clinically significant active infection within 1 week (i.e. chronic infections including Hepatitis B/C or HIV or acute infections, including urinary tract infection and respiratory tract infection)
- Received an agent not approved by the FDA for marketed use in any indication or any small molecule inhibitors (i.e. naltrexone) within 60 days of enrollment.
- Subjects who are taking greater than 20 mg (or if body weight <40 kg, 0.5 mg/kg) of prednisone daily.
- Clinically significant abnormal biochemical and hematological parameters, including:
 - Neutrophil count < 1000 cells/mm³
 - Hemoglobin < 8 g/dl
 - Platelet count ≤ 130 cells/mm³
 - Creatinine ≥ 1.2 x the upper limit of normal
 - Alanine aminotransferase (ALT) and/or aspartate aminotransferase (AST) ≥ 2x the upper limit of normal
 - Conjugated bilirubin greater than 1.2 mg/dL
- Has active infection with enteric pathogens as evidenced by positive microbiological culture of stool or C.difficile toxin PCR.
- Had bowel surgery other than perianal procedures (fistulotomy, seton placement, abscess drainage) within 3 months of enrollment.
- Has uveitis
- Has known pulmonary disease, excluding mild intermittent asthma

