7 STATISTICAL CONSIDERATIONS

7.1 Statistical Analysis Plan

7.1.1. Sample size and follow up. A maximum of 6 patients will be treated in this pilot study. It is anticipated that it will require 18-24 months to accrue 6 patients. With the additional 24 months of follow up to evaluate efficacy endpoints noted in Section 2, the anticipated trial duration will be 48 months.

7.1.4. Safety Monitoring and Stopping Rules. For the purpose of safety monitoring, "toxicity" will be defined as a probable or definite regimen related severe (grade 3 or worse) adverse event occurring at any time from the start of therapy to 45 days following the last MSC administration. If we observe 1 severe (grade 3 or worse) adverse event occurring at any time from the start of therapy to 45 days following the last MSC administration in the young adult cohort we will stop the study. If we observe no attributable severe adverse events in the young adult cohort, but do observe 1 severe (grade 3 or worse) adverse events occurring at any time from the start of therapy to 45 days following the last MSC administration in the pediatric cohort, we will stop the study.

7.1.3. Future Trials. If the trial is not stopped early, then the toxicity and efficacy data will be used to plan a future trial of MSC cell therapy in pediatric patients with either CD or UC, including (i) blinded placebo-controlled phase II trials optimizing dose or administration schedule, or (ii) randomized comparison to standard therapies.

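### The numeric platelet exclusion is printed with a value and unit that do not agree, in both eligibility lists, so the number itself screens out effectively nobody

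*Protocol*

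**What the plan says.** Section 2.6.2 of the protocol excludes patients under the lead-in "Clinically significant abnormal biochemical and hematological parameters, including", followed by six laboratory limits. Two of them are cell counts in the same unit: "Neutrophil count < 1000 cells/mm³" and, two lines below with hemoglobin between them, "Platelet count ≤ 130 cells/mm³". The exclusion list in the synopsis prints the platelet line in identical form. The protocol contains no other platelet threshold, no laboratory reference range and no note on units.

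The limit is meant to be used. Table 1 (section 3.6) schedules a CBC at screening and on each infusion day, with an eligibility check on Day 0. Section 3.8 lists eligibility criteria among the activities for Days 0, 7, 14 and 21. Section 9 requires an eligibility checklist for each patient, though the checklist is not reproduced. On trial size, section 7.1 states: "A maximum of 6 patients will be treated in this pilot study".

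**The concern.** A platelet limit of 130 in a unit of single cells per mm³ is far below any count normally met in clinical practice. It is also smaller than the neutrophil limit given in the same unit in the same list. Because the synopsis and section 2.6.2 carry the same figure, neither corrects the other.

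This is an operative eligibility threshold, not background text. If the number has no practical effect, platelet screening moves from a fixed rule to case-by-case judgment, and the protocol does not say what count should prompt it. Staff who read in a multiplier are applying a criterion that is not written down. Staff who read the line literally have no working numeric limit. Blood counts matter in this population: section 2.6.1 allows patients on methotrexate or 6MP/azathioprine, and section 1.2 names bone marrow suppression among the possible effects of methotrexate.

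**Working it through.** No sample size, power or error-rate figure is involved. The check is one of units and scale.

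**Inputs from the protocol**
- Platelet limit: 130 cells/mm³ (section 2.6.2, and identically in the synopsis).
- Neutrophil limit: 1000 cells/mm³ (same list, same unit).

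**Inputs assumed, because the protocol gives none**
- Platelets number in the tens to hundreds of thousands per mm³.
- Ordinary lower limit of normal: 130,000 to 150,000 per mm³.
- Profound thrombocytopenia: 10,000 to 20,000 per mm³.

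**Step 1, unit conversion.** 1 mm³ = 1 µL, so 130 cells/mm³ = 130 cells/µL = 0.13 × 10³/µL = 0.13 × 10⁹/L.

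**Step 2, comparison inside the list.** 130 / 1000 = 0.13, so the platelet limit as printed is about one eighth of the neutrophil limit. These are different cell types, so this ratio alone proves nothing. It only prompts the scale check.

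**Step 3, against the assumed lower limit of normal.**
- 130 / 130,000 = 0.10%
- 130 / 150,000 = 0.09%

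The printed limit is about 1,000 times lower (1,000 to 1,154 times).

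**Step 4, against assumed profound thrombocytopenia.**
- 10,000 / 130 = 77
- 20,000 / 130 = 154

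A patient with either count is far above the printed limit and does not meet the numeric exclusion.

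**Step 5, could another passage rescue the figure?** The two lists agree with each other and no other passage gives a platelet limit. A multiplier lost when the PDF was read cannot be ruled out completely. It is unlikely, because the wording is the same in two separate lists and the superscript in the unit survived in both.

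**The case against.** The strongest reply is that the error is conspicuous and surrounded by other safeguards. The lead-in "Clinically significant abnormal biochemical and hematological parameters, including" makes the six limits examples, so an investigator may still exclude a patient whose low platelet count is clinically significant. A CBC is scheduled on every infusion day. Section 6 allows withdrawal for a laboratory abnormality that makes continued participation contrary to the subject's interest, for a pre-treatment change that breaches eligibility, or when the investigator judges the subject unfit. Clinicians would probably notice the slip. It alters no endpoint, analysis, sample size or stopping boundary.

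All of this stands, and it limits the point to the numeric limit. It does not make the printed line right: these routes depend on judgment, and a stated number is there so that this part of screening does not.

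Three stronger readings might be inferred, and the protocol supports none of them.
- **That a thrombocytopenic patient would simply be enrolled and infused.** The lead-in and section 6 leave room to exclude or withdraw such a patient.
- **That the slip raises the chance of triggering the stopping rule.** No passage links platelet count to severe events after MSC infusion. Section 7.1 is also not clear on whether a stopping event must be attributed to the regimen: its definition of toxicity requires probable or definite attribution, while the stopping sentences that follow do not consistently repeat it.
- **That a multiplier of a thousand was certainly dropped and should be put back.** This is the likely explanation, but the protocol does not show whether the number, the unit or a multiplier is wrong.

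Nor can one say that the eligibility checklist repeats the slip, because it is not shown.

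**Conclusion.** The point holds for the numeric criterion. As printed in both lists, the platelet value and its unit do not agree, and the limit excludes effectively no candidate. A count of 130 per mm³ or less is logically possible, but it amounts to having almost no platelets.

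The conclusion rests on general knowledge of platelet scale, stated as an assumption because the protocol has no reference range. It is not sensitive to the exact figure assumed: at any count in the tens of thousands or above, the printed limit has no effect. The factor of 1,000 is conditional on thousands per mm³ having been intended. What remains as written is exclusion by judgment. This is a wrong decision figure in a safety-screening rule and should be corrected, although no statistical result depends on it.

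**What to change.** The sponsor should confirm the intended platelet threshold and its unit from its own records, then correct the line in the synopsis exclusion list and in section 2.6.2 together, so that value and unit agree and the two lists match. The eligibility checklist required by section 9 should be checked against the corrected text. No threshold is proposed here, because the protocol does not establish one.

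The cost is one line in two places plus a check of one form. No visit, blood draw or test is added, since a CBC is already done at screening and on Day 0, and no change to the sample size or analysis follows.

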3 STUDY AGENT

3.1 Preparation Administration, and Dosage

On the day of each infusion, the following procedures/assessments will be performed:

- MSCs will be thawed, harvested, counted, the viability will be determined, and appropriate samples will be sent for other release testing (including sterility). Vital signs (heart rate, blood pressure, respiratory rate, and temperature) will be measured within 15 minutes prior to the infusion (time 0) and then every 5 minutes during the infusion. If vital signs are normal after three 5-minute checks, they will be checked every 15 minutes during the remainder of the infusion, and then at 30 and 60 minutes after the infusion for 1 hour.
- Patients will be monitored according to institutional standards for administration of blood products and at a minimum will be monitored according to below:
 - Patients should remain in the clinic for at least one hour
 - Patients should remain on continuous pulse oximetry for at least 30 minutes

- Vital signs should be monitored at the end of the infusion then at 30 and 60 minutes
- Per institutional guidelines, pre-medication, consisting of oral acetaminophen (10-15 mg/kg/dose, max 650 mg) and diphenhydramine (0.5-1 mg/kg/dose, max 50 mg), will be administered at least 30 minutes prior to the infusion.
- No other medications should be given during the infusion, unless determined medically necessary by the treating physician.
- Supplemental oxygen will be kept by the bedside at all times.
- MSCs suspended in Plasmalyte A (multiple electrolyte injection) will be given as an IV infusion using weight-based dosing. We plan to infuse $1-4 \times 10^6$ cells per mL, not to exceed 240 mL. With a mean weight of 40 kg, the infusion volume would be 40-120 mL.
- Cells will be infused on Day 0 followed by repeat infusions weekly over a total of 4 weeks. An additional 4 weekly doses may be infused at discretion of physician. An attempt will be made to administer repeat infusions from the same initial donor, but administration of MSCs from another donor is permitted if same-donor cells are unavailable. Tracking of donor sample identification information will be performed for each sample.
- MSC's will be administered intravenously via a 18 gauge needle at a controlled rate of 4-6 ml/minute via infusion pump for patients weighting 35 kg or more. For patients under 35 kg in weight, the infusion will run in over 60 minutes at a rate no greater than 4-6 ml/minute. A syringe in combination with syringe pump can be used for administration in smaller patients.
- During the administration, the infusion must be stopped for any of the following reasons:
 - If the patient has symptoms or signs of respiratory difficulty, including but not limited to tachypnea, cyanosis, complains of shortness of breath, even if the pulse oximeter reading is normal. If the symptoms resolve within 30 minutes after standard supportive oxygen therapy, the infusion may be resumed at half the initial rate and the infusion must be completed within 2 hours of starting the infusion. If the symptoms recur, then the infusion will be stopped and will not be resumed.
 - If SaO_2 decreases to $\leq 90\%$ over a continuous period of > 3 minutes, whether or not the patient has symptoms of respiratory distress. If the SaO_2 is $\leq 90\%$ in the absence of symptoms or signs, the accuracy of the pulse oximeter reading should be confirmed by using another machine, relocating the sensor, or testing the device on another patient.
 - Infusion may be stopped at the discretion of the treating physician if there is another AE that the treating physician believes is related to the infusion, or if there is an issue with the infusion, or if the patient withdraws consent.

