Study Design: This study is a pilot phase 1 study of patients with moderately to severely active Crohn Disease (CD) and ulcerative colitis (UC) (≥ 18 years, Mayo score: ≥ 6 or CDAI: > 220 ; < 18 years, Pediatric Crohn's Disease Activity Index (PCDAI) > 30) or Pediatric Ulcerative Colitis Activity Index (PUCAI) > 34). [1] [2] A fixed dose will be studied: 1×10^6 cells/kg administered intravenously (IV) weekly for 4 consecutive weeks, with the option of an additional 4 weeks of treatment, at the discretion of the principal investigator. The primary outcomes are regimen-related toxicity, defined in section 5. Toxicity will be scored as a binary variable indicating occurrence or non-occurrence over a monitoring interval from the start of MSC therapy to 45 days after the last infusion. Based on the planned administration schedule of 4 weeks, the total toxicity monitoring period will have duration $28 + 45 = 73$ days. If additional weekly doses are administered, the safety assessment phase will be 45 days after the last dose given.

Three young adult patients (ages 17≤22 years) will be enrolled, staggered by at least 7 days, and monitored for toxicity over a period of 73 days. Infusions are administered over the first 28 days, followed by a 45 day monitoring period. If we observe no severe (grade 3 or worse) adverse events in the young adult cohort, we will wait a minimum of 45 days after the last MSC administration before beginning to enroll 3 more patients, ages 12≤16 (pediatric cohort). If we observe a severe (grade 3 or worse) adverse event occurring at any time from the start of therapy to 45 days following the last MSC administration in the young adult cohort we will stop the study. If we observe no severe adverse events attributable to MSCs in the young adult cohort but a severe (grade 3 or worse) adverse event occurring at any time from the start of therapy to 45 days following the last MSC administration in the pediatric cohort we will stop the study. A maximum of 6 patients will be enrolled. Assuming an accrual rate of 3-4 patients per year, it is anticipated that it will require at least 18-24 months to accrue all 6 patients.

Eligibility

This protocol allows for the treatment of both male and female pediatric and young adult patients, between the ages of 12 ≤ 22 years, with active moderate to severe CD or UC, who have failed to respond to, or are intolerant of, biologic therapy.

Inclusion criteria

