In our study, toxicity will be scored as a binary variable indicating occurrence or non-occurrence over a monitoring interval from the start of MSC therapy to 45 days after the last infusion. Based on the planned administration schedule, the total toxicity monitoring period will have duration $28 + 45 = 73$ days. If we observe no severe (grade 3 or worse) adverse events in the young adult cohort, we will wait a minimum of 45 days before beginning to enroll 3 more patients, ages $12 \leq 16$ years (pediatric cohort). If we observe a severe (grade 3 or worse) adverse event occurring at any time from the start of therapy to 45 days following the last MSC administration in the young adult cohort we will stop the study. If we observe no SAEs attributed to MSC administration in the young adult cohort but an SAE (grade 3 or worse) occurring at any time from the start of therapy to 45 days following the last MSC administration in the pediatric cohort, we will stop the study. If patients with active disease do not have >grade 2 toxicity attributed to

cells and fail to rapidly progress with disease requiring urgent therapy or surgery, and at the discretion of the principal investigator, 4 additional weekly doses may be administered. Subjects are eligible to receive up to 4 additional doses of MSCs at weekly intervals, each of which will consist of the same cell number (1×10^6 cells/kg). The safety assessment period will be 45 days from the last dose administered. A maximum of 6 patients will be enrolled. Assuming an accrual rate of 3-4 patients per year, it is anticipated that it may require at least 18- 24 months to accrue all 6 patients. With the additional 24 months of follow up to evaluate longer-term safety and efficacy endpoints, the anticipated trial duration will be about 48 months.

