1.4.3 Rationale for the Dosage and Treatment Period

Our chosen dose 1×10^6 cells/kg weekly x 4 weeks is within the dosing parameters of previous trials. In trials of MSCs in pediatric GVHD, doses as high as 8×10^6 cells/kg/dose were given up to twice per week for four weeks. [51] The rate of

administration (for patients < 35 kg, total infusion over 60 minutes, and for children ≥ 35 kg, 4-6 ml/minute via infusion pump) is also consistent with prior pediatric administration in patients with GVHD. [51]

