2.2 Study Design

This study is a pilot phase 1 treatment protocol for subjects with moderate to severe CD or UC who have failed to respond to or are intolerant of a biologic. Patients must have had a flexible sigmoidoscopy, colonoscopy or MR enterography within 2 months of enrollment, demonstrating active inflammatory disease.

Two types of patients will be enrolled:

- Moderate to severely active CD subjects (defined in Section 2.4)
- Moderate to severely active UC subjects (defined in Section 2.4)

At the beginning of the trial, a history and physical examination will be obtained, and documentation of baseline co-variates[52]:

CD:

- age
- gender

BMSCs

- ethnicity
- history of abdominal surgery
- duration of time with diagnosis
- age at diagnosis
- disease location
- history of failed biologic use
- history of stricturing/penetrating disease
- positive family history of IBD
- history of perianal disease
- severity and phenotype (Montreal classification for adults, or Paris classification for children)

UC:

- age
- gender
- ethnicity
- age at diagnosis
- history of failed biologic use
- duration of time since diagnosis
- positive family history of IBD)

During the course of the patient's treatment with MSCs, standard of care will be administered by the treating physician, at his/her discretion. There are no specific or "antidotal" therapies. Thus, any toxicity that arises during a patient's participation in this treatment will be managed with supportive measures at the discretion of the treating physician.

Three young adult patients (ages 17≤22 years) will be enrolled, staggered by at least 7 days between patients, and each monitored for toxicity over a period of 73 days. A fixed dose will be studied: 1×10^6 cells/kg administered intravenously (IV) weekly for 4 consecutive weeks. Infusions are administered over the first 28 days, followed by a 45 day monitoring period. The primary outcome is regimen-related toxicity, defined in section 5. Toxicity will be scored as a binary variable indicating occurrence or non-occurrence over a monitoring interval from the start of MSC therapy to 45 days after the last infusion. Based on the planned administration schedule, the total toxicity monitoring period will have duration $28 + 45 = 73$ days.

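### Section 3.1 gives an infusion volume of 40-120 mL at 40 kg, but the protocol's own dose and cell concentration give 10-40 mL

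*Protocol*

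**What the plan says.** The protocol has one dose level. The synopsis states: "A fixed dose will be studied: 1×10^6 cells/kg administered intravenously (IV) weekly for 4 consecutive weeks". Section 2.2 repeats it, section 1.4.3 justifies that single dose, and section 1.4.2 says of the optional further infusions that "each of which will consist of the same cell number" applies, again at 1×10^6 cells/kg.

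Section 3.1 covers preparation and administration. On each infusion day "MSCs will be thawed, harvested, counted, the viability will be determined". The product "will be given as an IV infusion using weight-based dosing". On concentration it says: "We plan to infuse $1-4 \times 10^6$ cells per mL", with a ceiling of 240 mL. It then gives the protocol's only worked volume: "With a mean weight of 40 kg, the infusion volume would be 40-120 mL".

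**The concern.** Dose per kg, weight, concentration and volume are tied by one equation, so once three are stated the fourth follows. Section 3.1 states all four, directly or by reference to the fixed dose, and the volume is not the one that follows from the other three.

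This is operative text, in the section that staff would use to prepare and give the cells. A product made exactly to the stated dose and concentration would fall below the example at every concentration above 1×10^6 cells/mL. If instead the stated volume were drawn up at the stated concentration, a patient would receive more than the fixed dose unless the product happened to be 40 mL at 1×10^6 cells/mL. In a study whose purpose is to assess the safety of one fixed dose, the text should not be open to two readings of how much is given.

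**Working it through.** **Inputs**

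| Quantity | Value | Where |
|---|---|---|
| Dose, D | 1×10^6 cells/kg | Synopsis; sections 1.4.2, 1.4.3, 2.2 |
| Concentration, C | 1-4×10^6 cells/mL | Section 3.1 |
| Weight, W | 40 kg | Section 3.1 |
| Stated volume | 40-120 mL | Section 3.1 |
| Volume ceiling | 240 mL | Section 3.1 |

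**Formula:** V = D × W / C.

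**Attempt to reproduce the stated figure**

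- Cells needed: 40 kg × 1×10^6 cells/kg = 40×10^6.
- At 4×10^6/mL: 40×10^6 / 4×10^6 = 10 mL.
- At 1×10^6/mL: 40×10^6 / 1×10^6 = 40 mL.

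The result is 10-40 mL, so the stated 40-120 mL is not reproduced. The lower end is 40/10 = 4 times and the upper end 120/40 = 3 times the derived value.

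**Concentration that the stated volumes would need at the fixed dose**

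- 40 mL: 40×10^6 / 40 = 1.0×10^6/mL.
- 80 mL: 40×10^6 / 80 = 0.5×10^6/mL.
- 120 mL: 40×10^6 / 120 ≈ 0.33×10^6/mL.

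Every stated volume above 40 mL lies outside the stated concentration range.

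**Dose delivered at 40 kg if the stated volume and concentration were both followed** (V × C / W)

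| Volume | at 1×10^6/mL | at 4×10^6/mL |
|---|---|---|
| 40 mL | 1×10^6/kg | 4×10^6/kg |
| 120 mL | 3×10^6/kg | 12×10^6/kg |

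The 12×10^6 entry is the extreme pairing only.

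**Could another reading rescue the sentence?**

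- *Another single dose.* At 40 kg, doses of 2, 3, 4 and 8×10^6/kg give 20-80, 30-120, 40-160 and 80-320 mL. None is 40-120. With one dose and one weight, a 4-fold concentration range must give a 4-fold volume range, and 120/40 is 3-fold.
- *Another single weight.* At the fixed dose, 120 mL at 1×10^6/mL fits 120 kg, while 40 mL at 4×10^6/mL fits 160 kg. No one weight fits both ends.
- *A spread of weights.* At 1×10^6/mL, 40-120 mL would match weights of 40 to 120 kg, but then 40 kg is the minimum and not the mean that the sentence names.
- *The 1-4×10^6 figure read as a per-kg dose at 1×10^6/mL.* This gives 40-160 mL.
- *A mistake in the upper concentration alone.* The largest volume depends only on the lowest concentration. With a floor of 1×10^6/mL, a 40 kg patient cannot exceed 40 mL.
- *Dilution or flush.* Section 3.1 gives the concentration as infused, and no such step is described.
- *The 240 mL ceiling.* At the fixed dose and lowest concentration it is reached only at 240 kg, so it explains nothing here.

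The figure does arise from inputs that the protocol does not state, such as 1-3×10^6 cells/kg at 1×10^6/mL, or 0.33-1×10^6 cells/mL at the fixed dose.

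**Side effect on duration.** At the 4-6 mL/minute that section 3.1 gives for patients of 35 kg or more, 10-40 mL runs in about 1.7 minutes (10/6) to 10 minutes (40/4), and 120 mL in 20 to 30 minutes (120/6 to 120/4).

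**The case against.** The best reply is that the sentence describes and does not instruct. The protocol expresses dose only in cells per kg, section 3.1 says that dosing is by weight, and cells are counted on each infusion day. To give 3 or 12 times the dose, staff would have to set aside both the prescribed dose and the count and treat an illustrative volume as a target. The 40-120 mL range is no release criterion. The only volume limit is the ceiling, and it is not in play. The concentration is itself worded as a plan, and if that is the loose figure, the delivered dose is as stated. Preparation instructions outside the protocol may well be correct.

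Much of this stands. An overdose is avoidable, the 12-fold figure is a worst case and no forecast, and the document does not show that preparation would go wrong. None of it restores the stated range. No dilution step, second dose level or redaction does so either. Dose, concentration and volume as written can be followed together at one point only, 40 mL at 1×10^6 cells/mL.

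**Conclusion.** The concern holds. At 40 kg the protocol's own inputs give 10-40 mL, and section 3.1 states 40-120 mL. The conclusion rests only on the fixed dose, the concentration as infused, and the 40 kg in the example; it needs no outside figure. The document does not show whether the volume, the concentration or the dose assumed behind the sentence is at fault.

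The consequence is limited. Endpoints, analyses and the stopping rule do not depend on the volume. It should nevertheless be corrected, because it is a definite numerical error in the section that governs how the product is prepared and given, and it bears on how much a patient receives.

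**What to change.** The sponsor should reconcile the dose (cells/kg), concentration (cells/mL) and volume (mL) statements so that dose × weight / concentration returns the printed volume at both ends of the concentration range. Section 3.1 should then carry a worked example that shows this. If a dilution, flush or other step lies behind the larger volumes, it should be written down. Which figure is right is for the sponsor to establish, and this review proposes none.

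The cost is an amendment to one paragraph of section 3.1, with no change to design, endpoints or analysis. Any preparation or administration instructions derived from that paragraph should be checked against the reconciled figures.
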